# Date

#### ETHICAL AND REGULATORY REQUIREMENTS 8.

#### 8.1 Ethical conduct of the study

The study will be performed in accordance with ethical principles that have their origin in the Declaration of Helsinki and are consistent with International Conference on Harmonisation (ICH)/Good Clinical Practice (GCP), applicable regulatory requirements and the AstraZeneca policy on Bioethics and Human Biological Samples.

#### 8.2 **Patient data protection**

The ICF will incorporate (or, in some cases, be accompanied by a separate document incorporating) wording that complies with relevant data protection and privacy legislation.

#### 8.3 Ethics and regulatory review

An Ethics Committee (EC) should approve the final CSP, including the final version of the ICF and any other written information and/or materials to be provided to the patients. The investigator will ensure the distribution of these documents to the applicable EC, and to the study site staff.

The opinion of the EC should be given in writing. The investigator should submit the written approval to AstraZeneca before enrolment of any patient into the study.

The EC should approve all advertising used to recruit patients for the study.

AstraZeneca should approve any modifications to the ICF that are needed to meet local requirements. Before enrolment of any patient into the study, the final CSP, including the final version of the ICF, is approved by the national regulatory authority or a notification to the national regulatory authority is done, according to local regulations.

AstraZeneca will handle the distribution of any of these documents to the national regulatory authorities.

AstraZeneca will provide Regulatory Authorities, ECs and PIs with safety updates/reports according to local requirements, including Suspected Unexpected Serious Adverse Reactions (SUSARs), where relevant.

#### 8.4 Informed consent

The PIs at each centre will.

- Ensure each patient is given full and adequate oral and written information about • the nature, purpose, possible risk and benefit of the study
- Ensure each patient is notified that they are free to discontinue from the study at any • time

Approved

AN

ЪО

PRINTED COPY

R

ы В

THIS

PLEASE CHECK ITS VALIDITY BEFORE USE

- Ensure that each patient is given the opportunity to ask questions and allowed time to consider the information provided
- Ensure each patient provides signed and dated informed consent before conducting any procedure specifically for the study
- Ensure that patient "E-code" has been entered on the ICF after enrolling the patient into the study
- Ensure the original signed and dated original ICF(s) is/are stored in the Investigator's Study File
- Ensure a copy of the signed ICF is given to the patient
- Ensure that any incentives for patients who participate in the study as well as any provisions for patients harmed as a consequence of study participation are described in the ICF that is approved by an EC

The potential patient or his/her guardian/legal representative should sign ICF before any study-specific procedures are performed, which include the following:

- Withholding or discontinuing of any treatment
- Endoscopy including treatment and photo
- Collection of blood
- ECG
- Pregnancy test

Those patients who are unconscious or considered by the investigator clinically unable to consent at Screening and who are entered into the study by the consent of a legally acceptable representative should provide their own written informed consent for continuing to participate in the study as soon as possible on recovery, as applicable in accordance with local regulations.

# 8.5 Changes to the protocol and informed consent form

Study procedures will not be changed without the mutual agreement of the National Coordinating Investigator and the PI and AstraZeneca.

If there are any substantial changes to the CSP, then these changes will be documented in a CSP amendment and where required in a new version of the CSP (Revised CSP).

The amendment is to be approved by the relevant EC and if applicable, also the national regulatory authority approval, before implementation. Local requirements are to be followed for revised protocols.

AstraZeneca will distribute any subsequent amendments and new versions of the protocol to each PI(s) for distribution to EC see Section 8.3.

If a protocol amendment requires a change to a centre's ICF, AstraZeneca and the centre's EC are to approve the revised ICF before the revised form is used.

If local regulations require, any administrative change will be communicated to or approved by each EC.

# 8.6 Audits and inspections

Authorised representatives of AstraZeneca, a regulatory authority, or an EC may perform audits or inspections at the centre, including source data verification. The purpose of an audit or inspection is to systematically and independently examine all study-related activities and documents, to determine whether these activities were conducted, and data were recorded, analysed, and accurately reported according to the protocol,GCP, guidelines of the ICH, and any applicable regulatory requirements. The investigator will contact AstraZeneca immediately if contacted by a regulatory agency about an inspection at the centre.

# 9. STUDY MANAGEMENT BY ASTRAZENECA

# 9.1 **Pre-study activities**

Before the first patient is entered into the study, it is necessary for a representative of AstraZeneca to visit the investigational study site to:

- Determine the adequacy of the facilities
- Determine availability of appropriate patients for the study
- Discuss with the investigator(s) (and other personnel involved with the study) their responsibilities with regard to protocol adherence, and the responsibilities of AstraZeneca or its representatives. This will be documented in a Clinical Study Agreement between AstraZeneca and the investigator

# 9.2 Training of study site personnel

Before the first patient is entered into the study, an AstraZeneca representative will review and discuss the requirements of the CSP and related documents with the investigational staff and also train them in any study specific procedures and the WBDC and IWR/IVRS utilised.

The PI will ensure that appropriate training relevant to the study is given to all of these staff, and that any new information relevant to the performance of this study is forwarded to the staff involved.

The Principal Investigator will maintain a record of all individuals involved in the study (medical, nursing and other staff).

Before the first patient is enrolled for the study, the investigational staff will have an opportunity to discuss the study assessments, procedures associated with the collection of blood samples, with AstraZeneca personnel.

Consistency in the classification of PUB at endoscopy is crucial, and in order to obtain objective measurements, training material will be provided by AstraZeneca to harmonize the endoscopic assessments across study sites.

# 9.3 Monitoring of the study

To maintain blinding of the IP, during the study, both blinded and unblinded monitor will have regular contacts with study sites:

The blinded monitor will:

- Provide information and support to the investigator(s)
- Confirm that facilities remain acceptable
- Confirm that the investigational team is adhering to the protocol, that data are being accurately and timely recorded in the clinical chart and the eCRFs, including the data entry of and responses to queries issued and samples are handled in accordance with the Laboratory Manual
- Perform source data verification (a comparison of the data in the eCRFs with the patient's medical records at the hospital or practice, and other records relevant to the study), including verification of informed consent of participating patients. This will require direct access to all original records for each patient (e.g., clinic charts)

The unblinded monitor will verify IP accountability from receipt of IP through declaration of clean file and data base lock (see Section 5.7.1).

The AstraZeneca monitor will be available between visits if the investigator(s) or other staff at the centre needs information and advice about the study conduct.

# 9.3.1 Source data

Refer to the Clinical Study Agreement/applicable information for location of source data.

#### 9.4 **Study agreements**

The PI at each/the centre should comply with all the terms, conditions, and obligations of the CSA, or equivalent, for this study. In the event of any inconsistency between this CSP and the CSA, the terms of CSP shall prevail with respect to the conduct of the study and the treatment of patients and in all other respects, not relating to study conduct or treatment of patients, the terms of the CSA shall prevail.

Agreements between AstraZeneca and the PI should be in place before any study-related procedures can take place, or patients are enrolled.

#### 9.4.1 Archiving of study documents

The investigator follows the principles outlined in the CSA.

#### 9.5 Study timetable and end of study

The end of the study is defined as Last patient last visit.

The study is expected to start in and to end by

Enrolment will be stopped when 200 evaluable patients have been randomised.

The study may be terminated at individual centres if the study procedures are not being performed according to GCP, or if recruitment is slow. AstraZeneca may also terminate the entire study prematurely if concerns for safety arise within this study or in any other study with esomeprazole. The rate of inclusion at the different sites will be encouraged and evaluated on a regular basis.

The planned overall timetable for the study is as follows:

First patient in

Last patient in

Last patient last visit

Database lock

#### 10. DATA MANAGEMENT BY ASTRAZENECA OR DELEGATE

Data management will be performed by the AstraZeneca Data Management Centre (DMC).

The data collected through third party sources will be obtained and reconciled against study data.

ЪО

PRINTED COPY

¢

5 H

THIS

AN ELECTRONIC DOCUMENT. PLEASE CHECK ITS VALIDITY BEFORE USE

PLEASE CHECK ITS VALIDITY BEFORE USE

ELECTRONIC DOCUMENT.

AN

ЪО

PRINTED COPY

К

ы И

THIS

AE and medical/surgical history will be classified according to the terminology of the latest version the Medical Dictionary for Regulatory Activities (MedDRA). Medications will be classified according to the AstraZeneca Drug Dictionary. All coding will be performed by the Medical Coding Team at the AstraZeneca DMC.

Data queries will be raised for inconsistent, impossible or missing data. All entries to the study database will be available in an audit trail.

The data will be validated as defined in the Data Management Plan (DMP). Quality control procedures will be applied to each stage of data handling to ensure that all data are reliable and have been processed correctly.

When all data have been coded, validated, signed and locked, clean file will be declared. Any treatment revealing data may thereafter be added and the final database will be locked.

Data associated with biological samples will be transferred to laboratories internal or external to AstraZeneca.

# 11. EVALUATION AND CALCULATION OF VARIABLES BY ASTRAZENECA

# **11.1** Calculation or derivation of efficacy variable(s)

# **11.1.1** Derivation or calculation of rebleeding variable

Rebleeding within 72 hours, 7 days and 30 days will be calculated from the date and time for significant rebleeding, as recorded in the eCRF.

# **11.1.2** Derivation or calculation of endoscopic re-treatment variable

Endoscopic re-treatment within 72 hours and 30 days will be calculated from the date and time for start of endoscopic re-treatment as recorded in the eCRF.

# **11.1.3** Derivation or calculation of surgery variable

Surgery within 72 hours and 30 days that is caused by rebleeding will be calculated from the date and time for start of such surgery as recorded in the eCRF.

# **11.1.4** Derivation or calculation of transfusion variable

The total amount of blood transfusions within 72 hours and 30 days will be calculated from the date, time and amount of blood transfusions as recorded in the eCRF.

# **11.2** Calculation or derivation of safety variable(s)

# 11.2.1 Other significant adverse events (OAE)

During the evaluation of the AE data, an AstraZeneca medically qualified expert will review the list of AEs that were not reported as SAEs and Discontinuation of IP due to adverse

57(65)

event(s) (DAEs). Based on the expert's judgement, significant AE of particular clinical importance may, after consultation with the Global Patient Safety Physician, be considered OAEs and reported as such in the CSR. A similar review of laboratory/vital signs data will be performed for identification of OAEs.

Examples of these are marked haematological and other laboratory abnormalities, and certain events that lead to intervention (other than those already classified as serious), dose reduction or significant additional treatment.

- **11.3** Calculation or derivation of patient reported outcome variables (Not applicable)
- 11.4 Calculation or derivation of pharmacokinetic variables (Not applicable)
- 11.5 Calculation or derivation of pharmacodynamic variables (Not applicable)
- 11.6 Calculation or derivation of pharmacogenetic variables (Not applicable)
- 11.7 Calculation or derivation of health economic variables (Not applicable)

# 12. STATISTICAL METHODS AND SAMPLE SIZE DETERMINATION

# **12.1** Description of analysis sets

# 12.1.1 Efficacy analysis set (Full Analysis Set)

All randomised patients, who started the randomised i.v. treatment (bolus dose), will be included in the FAS. The FAS data will be analysed as randomised, ie, patients are analysed based on their randomised treatment. Randomised treatment is defined as the treatment associated with the randomisation code given to the patient, identified via the randomisation schedule. The FAS will be used in the analysis of the primary objective and all other efficacy analyses.

# 12.1.2 Safety analysis set

All patients who received at least one dose of IP and for whom any post-dose data are available will be included in the safety population. Throughout the safety results sections, erroneously treated patients (eg, those randomised to treatment A but actually given treatment B) will be accounted for in the actual treatment group.

# 12.2 Methods of statistical analyses

The efficacy variable, rebleeding within 72 hours, will be presented using descriptive statistics by treatment group, baseline Forrest class and type of endoscopic treatment. Rebleeding events for the other time points, need for endoscopic re-treatments or surgery due to rebleeding, and number of blood units transfused will be handled in a similar fashion.

The rebleeding variable will also be analysed descriptively in subgroups based on age (up to or above 65 years) and gender.

Patients who leave the study prematurely without having had rebleeding will be included in the analysis and considered to have had no rebleeding.

Safety variables for the two groups will be presented using descriptive statistics.

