# 13(65)

## **1. INTRODUCTION**

#### 1.1 Background

Peptic ulcer bleeding (PUB) is the main cause of non variceal upper gastrointestinal bleeding, which is associated with considerable morbidity and mortality with reported incidence ranging from 48 to 160 cases per 100 000 adults per year (Barkun et al 2010). Although the incidence of peptic ulcers has decreased substantially over the last decades, PUB has not and mortality remains an issue with reported rates at 5 to 14% in population based epidemiological studies, and pooled rates of approximately 4% in recent interventional clinical trials with PPIs (Blatchford et al 1997, van Leerdam et al 2003, Leontiadis et al 2006, Barkun et al 2010). Hence, the mortality rate within 30 days in these patients is approximately 5-10%. These figures are remarkably unchanged during the last 30 years in spite of the introduction of more effective drugs in ulcer treatment such as Histamine type 2-Receptor Antagonists (H2RA) and Proton Pump Inhibitors (PPIs) in this period of time. Partial explanations to this apparent paradox are the increased use of Non-Steroidal Anti-Inflammatory Drugs (NSAIDs) and the increasing mean age of the population in the same time period. The risk of mortality depends on age, the presence or absence of comorbidities, the severity of the actual bleeding, and the occurrence of rebleeding (Holster and Kuipers 2011). Endoscopic haemostatic therapy is the cornerstone in treatment of high risk PUB patients. Despite this treatment rebleeding occurs in about 10 to 20% of the cases during the first month after the initial bleeding episode (Leontiadis et al 2006). Rebleeding has been reported to increase the risk for morbidity and fatal outcome, the need for repeated endoscopic treatment and surgery and to prolonged hospitalisation, particularly in patients with significant comorbidity (Rockall et al 1996, Kupfer et al 2000, van Leerdam et al 2003).

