# 5.8 Discontinuation of investigational product

Patients may be discontinued from study treatment at any time. Reasons for discontinuing a patient from IP may be:

- Patient decision. The patient is at any time free to discontinue treatment, without prejudice to further treatment
- Safety reasons as judged by the investigator and/or AstraZeneca (eg, histologically confirmed malignancy if routine biopsies were taken at visit 1)
- Adverse event, including event of rebleeding
- Eligibility criteria not fulfilled (see Section 5.3)
- Severe non-compliance to protocol as judged by the investigator and/or AstraZeneca
- Other reason specified by the investigator or AstraZeneca

If the patient is discontinued from IP, the scheduled study visits, data collection and procedures should continue according to the CSP until the follow-up visit. Alternatively, if the patient does not agree to this option, a modified follow up through e.g. telephone contact at the time-point of the follow-up visit should be arranged, if agreed to by the patient and in compliance with local data privacy laws/practices.

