# 5.9 Withdrawal from study

Patients are at any time free to withdraw from study (IP and assessments), without prejudice to further treatment (withdrawal of consent). Such patients will always be asked about the reason(s) and the presence of any AE. If possible, they will be seen and assessed by an investigator and the assessments specified for the final visit should be completed and recorded in the eCRF. Patient diary and all IPs should be returned by the patient. AEs will be followed up by the investigator for as long as medically indicated, but without further recording in the eCRF (see Sections 6.4.3 and 6.4.4).

Reasons for withdrawal from the study may include, but are not limited to

- Patient decision. The patient is at any time free to discontinue their participation in the study, without prejudice to further treatment.
- Eligibility criteria not fulfilled
- Death
- AE
- Severe non-compliance with protocol, defined as refusal or inability to adhere to the CSP requirement
- Patient lost to follow-up
- Other, with specification given.

Withdrawn patients will not be replaced. For all patients who have received IP but have discontinued from the study, the investigator should make every possible effort to check that the patient is not reported dead within 30 days after randomisation.

Date

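### Patients who leave the study alive without a recorded rebleed are counted as free of rebleeding, which can only lower the reported rates: little at 72 hours, more at 30 days

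*Protocol*

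**What the plan says.** - **The rule.** Protocol Section 12.2: "Patients who leave the study prematurely without having had rebleeding will be included in the analysis and considered to have had no rebleeding." No time point is named.
- **The variable.** Section 11.1.1: "Rebleeding within 72 hours, 7 days and 30 days will be calculated from the date and time for significant rebleeding, as recorded in the eCRF." A rebleed that never reaches the eCRF cannot count.
- **The denominator.** Section 12.1.1: "All randomised patients, who started the randomised i.v. treatment (bolus dose), will be included in the FAS." Leavers therefore stay in the denominator at every time point.
- **Who leaves.** Section 5.9 opens its list with "Reasons for withdrawal from the study may include, but are not limited to". The list includes patient decision, adverse event, death and loss to follow-up. It adds: "Withdrawn patients will not be replaced."
- **What happens after leaving.** Section 5.9 asks for a final assessment if possible. For treated patients who leave, "the investigator should make every possible effort to check that the patient is not reported dead within 30 days after randomisation". Adverse events are followed further but no longer entered in the eCRF. No later check for rebleeding is required.
- **Who does not leave.** Under Section 5.8, for a patient who only stops treatment, "the scheduled study visits, data collection and procedures should continue according to the CSP until the follow-up visit", with a telephone alternative. Section 5.8.1 requires rebleeding data for these patients.

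**The concern.** The rule turns an unknown outcome into a favourable one. A patient discharged and lost on day 4 enters the 30-day analysis as a full 30 days without rebleeding.

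The design makes unseen rebleeds possible after the infusion. Patients may go home once the infusion has ended and their condition allows, and the next scheduled visit is day 30 (+5). In between, rebleeding comes to light only if the patient makes contact (Sections 3.1 and 6.3.1.1).

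The absolute rates are the efficacy result here. The study makes no formal test and asks whether Chinese outcomes resemble those of the global study (synopsis, Statistical methods; Section 1.2). An error that can run in only one direction bears directly on that reading. It can also create a difference between arms if the arms lose patients at different rates.

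**Working it through.** **Plan's own figures.** The sample size is 100 per arm: 2 × 100 = 200, and 20 centres × 10 = 200, which agree. It rests on a safety and regulatory rationale, with no dropout rate, so there is no planned figure for this rule to reproduce.

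**Inputs from the protocol.** 72-hour rebleeding was 5.9% on esomeprazole in the global study (Section 1.1). Rebleeding in the first month is about 10% to 20% (Section 1.1). There are 100 patients per arm (Section 12.3).

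**Assumed inputs.** *d* is the share leaving alive, *f* the share of their risk still ahead when they leave, and *k* their risk relative to other patients. With *p* the rate in patients who stay:

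- Reported rate = p(1 − d) + k·p·d·(1 − f)
- True rate = p(1 − d) + k·p·d
- Bias = reported − true = −k·p·d·f

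The bias is never positive. It is zero only if no leaver rebleeds afterwards.

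| Time | p | d | f | k | Reported | True | Bias (points) |
|---|---|---|---|---|---|---|---|
| 72 h | 5.9% | 2% | 0.5 | 1 | 5.84% | 5.90% | −0.06 |
| 72 h | 5.9% | 5% | 1 | 1 | 5.60% | 5.90% | −0.30 |
| 72 h | 5.9% | 5% | 1 | 3 | 5.60% | 6.49% | −0.89 |
| 30 d | 10% | 10% | 0.5 | 1 | 9.5% | 10.0% | −0.5 |
| 30 d | 10% | 10% | 1 | 1 | 9.0% | 10.0% | −1.0 |
| 30 d | 20% | 10% | 1 | 1 | 18.0% | 20.0% | −2.0 |
| 30 d | 10% | 10% | 1 | 3 | 9.0% | 12.0% | −3.0 |
| 30 d | 20% | 10% | 1 | 3 | 18.0% | 24.0% | −6.0 |

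**Timing of loss.** f = 1 means leaving before any risk has passed, so it is the upper end for a given *d* and *k*. Suppose instead that all 10% leave at 72 hours and that 5.9% is taken as the risk already passed. The 30-day bias at average risk is then 0.10 × (10 − 5.9) = 0.41 points to 0.10 × (20 − 5.9) = 1.41 points.

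**Difference between arms.** With p = 10%, k = 1, f = 1 and leaving of 2% against 10%, the rule alone creates 10 × (0.10 − 0.02) = 0.8 points.

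**Bounds per 100 patients** (leaver counts assumed, all without a recorded rebleed):

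| Recorded rebleeds | Leavers | Rule | Leavers excluded | All leavers rebled |
|---|---|---|---|---|
| 6 | 5 | 6% | 6/95 = 6.3% | 11% |
| 6 | 10 | 6% | 6/90 = 6.7% | 16% |
| 10 | 5 | 10% | 10/95 = 10.5% | 15% |
| 10 | 10 | 10% | 10/90 = 11.1% | 20% |

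The reported rate does not change with the number who leave. For scale, the exact 95% interval is 2.2% to 12.6% for 6/100 and 4.9% to 17.6% for 10/100.

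**Deaths.** With death without rebleeding as a competing event and no censoring, cumulative incidence equals recorded rebleeds divided by patients, which is the proportion Section 12.2 reports. Such deaths do not bias it.

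**The case against.** **Death.** A reader might infer that every early leaver, deaths included, is wrongly scored, and that all three rates are biased for that reason. Section 1.1 invites this, since it says that "the mortality rate within 30 days in these patients is approximately 5-10" per cent. The documents do not support it. The variable is rebleeding, and a patient who dies without rebleeding did not rebleed. Death lowers the rate only if a fatal bleed was never recorded under the criteria in Table 3. Setting 30-day deaths beside the 5.9% rate would also mix time windows, because 5.9% is a 72-hour rate. This objection stands.

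**Who is covered.** The rule spares patients with a recorded rebleed, and those who only stop treatment remain in follow-up. Discharged patients receive an information card and are told to make contact. This stands, and it narrows the point to patients lost or withdrawn alive.

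**The primary endpoint.** Vital signs, Hb and Hct are checked every 8 hours during the infusion. A reader might note that five leavers scored the other way would move 5.9% to 10.9%. That needs five patients per 100 to leave within 72 hours and all of them to rebleed unseen, so it is an extreme bound. This also stands.

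**Comparability.** The documents do not say how the global study handled leavers. If it used the same rule, keeping the rule helps the comparison. That is a reason to retain it as a sensitivity analysis. It does not make the rule an unbiased estimate of the rate.

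**The SAP.** Sensitivity and disposition tables are commonly left to a SAP, which is not shown, and their absence is no fault. The rule itself, however, is fixed in the protocol.

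**Censoring has its own assumption.** It treats leaving as unrelated to rebleeding risk. That is true, and it is why a bound should accompany it.

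**Conclusion.** The point holds for patients lost or withdrawn alive. Section 12.2 scores their unknown later course as no rebleeding, and Section 5.9 does not seek rebleeding after they leave, so any error is downwards.

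- **72 hours:** about 0.1 to 0.3 points with 2% to 5% leaving at average risk, far inside sampling error. The primary result is barely touched.
- **30 days:** about 1 to 2 points if 10% leave early at average risk and the 30-day rate is 10% to 20%. It is less if they leave later, and 3 to 6 points if leavers carry three times the risk.
- **7 days:** exposed to losses after discharge. The protocol gives no 7-day rate, so no size is worked out here.

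Dropout, timing and relative risk are all assumptions, because the protocol states none of them. Severity is moderate: the rule should be changed, mainly for the secondary 7- and 30-day rates, but it does not undermine the primary description.

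**What to change.** In Section 12.2:

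1. Estimate the rebleeding rates, above all at 7 and 30 days, as cumulative incidence from the start of i.v. treatment, censored at last contact, with death without rebleeding as a competing event.
2. Keep the current rule as a sensitivity analysis, for comparability with the global study.
3. Add a bound that scores leavers with unknown outcome as rebleeds.
4. Report leavers and deaths by arm and time window beside each rate.
5. Count deaths attributed to bleeding as rebleeds in a sensitivity analysis only. In the main analysis this would add a criterion that Table 3 does not contain.

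**Cost.** A wording change and a few more tables. The times of rebleeding and the date and probable cause of death are already collected, and last contact can be taken from the last recorded visit or assessment. The reported rates may become slightly less favourable.
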